12. STATISTICAL CONSIDERATIONS

12.1 Study Design/Endpoints

This is a Pilot and Phase II, single-arm, open-labeled, multi-center study of entinostat in combination with anastrozole/tamoxifen in women with triple negative breast cancer. The main objective of this study is to assess the safety and efficacy of the combination of entinostat and anastrozole/tamoxifen. The primary endpoints, that we will use to evaluate the efficacy of the entinostat and anastrozole/tamoxifen, are the reduction in proliferative index (Ki67) and upregulation of ER after treatment with entinostat and anastrozole/tamoxifen therapy. We define patient's response as at least 50% reduction in the Ki67 index AND greater than 1% ER-positivity OR pathologic complete response in the post-treatment surgical specimens. For the evaluation of these biological endpoints, the analysis will include ALL of the patients in both cohorts (the first cohort-operable stage I-II and the second cohort-unresectable locally advanced/metastatic) as well as both anastrozole and tamoxifen groups.

In the pilot phase, the classic cohort-of-3-study design will be used. The primary endpoint of this part of the study is to determine the recommended dose for the phase II part as well as to evaluate the safety of both combinations. The dose levels are defined below for both pre- and postmenopausal groups. For safety, each combination (entinostat and anastrozole as well as entinostat and tamoxifen) will be evaluated separately. For both groups (anastrozole and tamoxifen), the first cohort of 3 patients will be treated starting at dose level 1 (d_1). If ≤ 1 patient experiences DLT, an additional 3 patients will be treated at this dose level (d_1). If ≥ 2 patients in the initial cohort of 6 patients suffer DLT, then up to 6 additional patients will be enrolled at the dose level -1. The phase II part will continue with the highest dose level with < 2 out of 6 patients experiencing a DLT. Therefore, we will need 6-12 patients for each combination

in this part of the study. The 6 patients from the pilot phase of each combination that are treated with the recommended dose level for the phase II will be included in the primary endpoint analysis.

The dose modification schemas are as follow for both postmenopausal and premenopausal women:

Dose Modification Schema for Postmenopausal Women		
Dose Level	Dose	
	Entinostat (mg)	Anastrozole (mg) daily
-1	3 mg weekly (on day 1, 8, 15, 22, and 29)	1
1	5 mg weekly (on day 1, 8, 15, 22, and 29)	1

or

Dose Modification Schema for Premenopausal Women		
Dose Level	Dose	
	Entinostat (mg)	Tamoxifen (mg) daily
-1	3 mg weekly (on day 1, 8, 15, 22, and 29)	20
1	5 mg weekly (on day 1, 8, 15, 22, and 29)	20

In the phase II part, the Simon's two-stage design will be used for the study to ensure that the number of patients exposed to this new treatment is minimized. The analysis for this part of the study will include ALL of the patients in both cohorts (the first cohort-operable stage I-II and the second cohort-unresectable locally advance/metastatic) as well as both anastrozole and tamoxifen groups. The total sample size for the phase II part of the study is 32 with 12 and 20 patients in the first and second stage respectively. The 6 patients in the pilot phase of each combination that are treated with the recommended dose level for phase II will be included in the first stage of the phase II part of the study. The study will be terminated, if there is no response among the first 12 patients. If ≥ 1 response in these 12 patients is observed, then 20 more patients will be accrued. The combination will be considered promising, if ≥ 4 out of 32 patients have a response. This design yields 87% power. The probability of early stopping and declaring that this combination has no sufficient activity is 0.54, if the true success rate is 5% and 0.07 if the true response rate is 20%. If the true proportion of patients with Ki67 reduction combined with ER up-regulation is 0.20, the probability of concluding that the drug has sufficient activity is 0.87 and 0.07 if the true proportion is 0.05. To allow about 10% inevaluability, the phase II trial will accrue 35 eligible patients. Statistical analysis will be done using S-plus (TIBCO, version 8.0). All descriptive statistics will be reported. The multivariate analysis of variance or its non-parametric alternative will be applied to compare biomarkers' expression levels. The 90% confidence intervals will be constructed for the observed proportions. All statistical tests will be two-sided, and done at the 0.05 level of significance.

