3. PATIENT SELECTION

3.1 Inclusion Criteria

- 3.1.1 Female greater than or equal to 18 years.
- 3.1.2 Eastern Cooperative Oncology Group (ECOG) performance status ≤ 2 (see Appendix A).
- 3.1.3 Histologically confirmed adenocarcinoma of the breast.
- 3.1.4 Evidence of hormone insensitivity (ER and PR negative) of primary tumor tissue. ER negative is defined as ER 0 or $< 1\%$ staining by immunohistochemistry. PR negativity is defined as PR $\leq 10\%$ staining by immunohistochemistry.
- 3.1.5 HER2 negative in the primary tumor tissue as defined by:
 - Immunohistochemistry (IHC) Grade 0 as defined by no staining observed or membrane staining that is incomplete and is faint/barely perceptible and within $\leq 10\%$ of the invasive tumor cell
 - IHC 1+ as defined by incomplete membrane staining that is faint/barely perceptible and within $> 10\%$ of the invasive tumor cell
 - IHC Grade 2+ staining intensity by means of IHC analysis with no gene amplification below.
 - No gene amplification on ISH based on
 - Single-probe average HER2 copy number < 4.0 signals/cell
 - Dual-probe HER2/CEP17 ratio < 2.0 with an average HER2 copy number < 4.0 signals/cell
- 3.1.6 Ability to understand and the willingness to sign a written informed consent document.
- 3.1.7 Patients must not have received any prior chemotherapy, radiation therapy, or endocrine therapy for their current breast cancer. Patients who received tamoxifen or raloxifene or another agent for prevention of breast cancer may be included as long as the patient has discontinued the treatment at least one month prior to baseline study biopsy.
- 3.1.8 Women of childbearing potential must have negative (serum or urine) pregnancy test within 7 days prior to registration.
- 3.1.9 Patients must have adequate tumor tissue sample prior to the enrolment available for correlative studies as defined below:
 - Core needle biopsy or incisional biopsy samples that can provide ≥ 3 unstained sections of 5 micron thickness. Fine needle aspiration (FNA) sample alone is not sufficient except in the second cohort.
 - Additional core needle biopsy needs to be performed in the patients who agree to participate in this study and do not have adequate tumor tissue sample.
 - 3.1.10 Patients must have adequate organ and marrow function as defined below:
 - Hemoglobin ≥ 9.0 g/dL
 - Leukocytes $\geq 2,500$ /mcL
 - Absolute neutrophil count $\geq 1,100$ /mcL
 - Platelets $\geq 100,000$ /mcL

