 - Total bilirubin within normal institutional limits
 - AST(SGOT)/ALT(SGPT) ≤ 2.5 x institutional upper limit of normal
 - Creatinine within normal institutional limits or creatinine clearance ≥ 60 mL/min/1.73 m² for patients with creatinine levels above institutional normal

Additional Inclusion Criteria for the First cohort:

- 3.1.11 Unresected operable breast cancer that meets the following clinical stages (see Appendix B):
 - T1b, T1c, or T2
 - N0 or N1
 - M0 (No distant metastasis)

Additional Inclusion Criteria for the Second cohort:

- 3.1.12 Unresectable, inoperable, recurrent local-regional breast cancer or
- 3.1.13 Metastatic (stage IV) breast cancer
- 3.1.14 Patients must have measurable or evaluable disease (i.e. ascites or pleural/pericardial effusion). Patients with bone metastatic only will be excluded.
- 3.1.15 Patients must not have rapidly progressive disease, extensive visceral involvement, or any high risk characteristics that are not appropriate for this treatment as per investigator's discretion.
- 3.1.16 Patients must receive at least one prior line of chemotherapy but not more 2 prior chemotherapy regimens for stage IV breast cancer. Prior chemotherapy in the adjuvant and /or neoadjuvant setting is permitted. However, patients must have finished chemotherapy at least 2 weeks prior to enrollment.
- 3.1.17 Patients must have an accessible tumor lesion from which a fine needle aspirate or preferably a core biopsy specimen can be obtained. Patients with FNA only samples are allowed in this cohort. Ascites or pleural/pericardial effusion alone is not sufficient.

- 3.1.18 Patients must be willing to provide consents for 2 research biopsies. However, the pretreatment biopsy can be omitted in patients who have recent biopsy but have not been started on breast cancer treatment within 12 weeks prior to the registration and there is adequate tumor tissue sample as per section 3.1.9.

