11.1.2 Pathologic Response

- Pathologic Complete Response (pCR): No viable invasive cancer in pathologic specimen, as determined by histological examination. We will report whether in situ disease only was present in the specimen versus no disease. We will also report for each woman whether she had a pCR in the breast only, in the lymph nodes only, or in both.
- Nodal Disease: We will report the number of women who had positive lymph node prior to starting study drugs, or at the time of surgery: 0, 1-3, 4-10, or >10 lymph nodes.

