APPENDIX B: American Joint Committee on Cancer Staging (AJCC)

T – Primary Tumor	
TX	Primary tumor cannot be assessed
T0	No evidence of primary tumor
Tis	Carcinoma in situ
Tis (DCIS)	Ductal carcinoma in situ
Tis (LCIS)	Lobular carcinoma in situ
Tis (Paget)	Paget's disease of the nipple with no tumor Note: Paget's disease associated with a tumor is classified according to the size of the tumor.
T1	Tumor ≤ 2 cm in greatest dimension
T1mic	Microinvasion ≤ 0.1 cm in greatest dimension
T1a	Tumor > 0.1 cm but not > 0.5 cm in greatest dimension
T1b	Tumor > 0.5 cm but not > 1 cm in greatest dimension
T1c	Tumor > 1 cm but not > 2 cm in greatest dimension
T2	Tumor > 2 cm but not > 5 cm in greatest dimension
T3	Tumor > 5 cm in greatest dimension
T4	Tumor of any size with direct extension to (a) chest wall or (b) skin, only as described below
T4a	Extension to chest wall, not including pectoralis muscle
T4b	Edema (including peau d'orange" or ulceration of the skin of the breast, or satellite skin nodules confined to the same breast
T4c	Both T4a and T4b
T4d	Inflammatory carcinoma

N – Regional lymph nodes	
NX	Regional lymph nodes cannot be assessed (e.g., previously removed)
N0	No regional lymph node metastasis
N1	Metastasis in movable ipsilateral axillary lymph node(s)
N2	Metastases in ipsilateral axillary lymph nodes fixed or matted, or in clinically apparent ipsilateral internal mammary nodes in the absence of clinically evident axillary lymph node metastasis
N2a	Metastasis in ipsilateral axillary lymph nodes fixed to one another (matted) or to other structures
N2b	Metastasis only in clinically apparent ipsilateral internal mammary nodes and in the absence of clinically evident axillary lymph node metastasis
N3	Metastasis in ipsilateral infraclavicular lymph node(s), or in clinically apparent ipsilateral internal mammary lymph node(s) and in the presence of clinically evident axillary lymph node metastasis; or metastasis in ipsilateral supraclavicular lymph node(s) with or without axillary or internal mammary lymph node involvement
N3a	Metastasis in ipsilateral infraclavicular lymph node(s) and axillary lymph node(s)
N3b	Metastasis in ipsilateral internal mammary lymph node(s) and axillary lymph node(s)
N3c	Metastasis in ipsilateral supraclavicular lymph node(s)

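### The pCR limb of the primary response does not require tumour to remain after the pre-treatment biopsy, so an unrecognised biopsy clearance of a small tumour would count as a drug response

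*Combined protocol and SAP*

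**What the plan says.** Section 12.1 sets the primary responder rule: "at least 50% reduction in the Ki67 index AND greater than 1% ER-positivity OR pathologic complete response in the post-treatment surgical specimens". On the ordinary reading, pCR is sufficient by itself, with no Ki67 or ER result needed.

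Section 11.1.2 defines pCR as "No viable invasive cancer in pathologic specimen, as determined by histological examination". It places no condition on what was in the breast when study drug began. It asks for a report of "whether she had a pCR in the breast only, in the lymph nodes only, or in both", but does not say which of these counts in the responder rule.

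Section 3.1.11 limits the first cohort to "Unresected operable breast cancer that meets the following clinical stages", with T1b the smallest. Appendix B defines T1b as "Tumor > 0.5 cm but not > 1 cm in greatest dimension". For pre-treatment tissue, section 3.1.9 accepts "Core needle biopsy or incisional biopsy samples that can provide" at least three unstained sections. When tissue is inadequate it adds: "Additional core needle biopsy needs to be performed in the patients who agree to participate in this study".

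Section 12.1 stops the trial at 0 responses in 12 and calls the combination promising at 4 or more in 32. It gives early-stopping probabilities of 0.54 and 0.07 at true rates of 5% and 20%, and go probabilities of 0.87 at 20% and 0.07 at 5%. The sentence with the go probabilities begins "If the true proportion of patients with Ki67 reduction combined with ER up-regulation is 0.20".

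**The concern.** If the biopsy happens to remove all the invasive tumour, the surgical specimen holds none. Ki67 and ER cannot then be scored, so the biomarker limb cannot be assessed, yet the pCR limb makes the patient a responder. The drug need have done nothing.

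No other provision closes the gap:

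- Breast imaging in section 4.2 is done as indicated, up to 6 weeks before entry, and is not tied to the biopsy.
- The clip in section 5.5.1 marks where the tumour was, not whether any remains.
- The inevaluable category in section 11.2.1 concerns palpation, not pCR.
- The 10% inevaluability allowance in section 12.1 is not defined in a way that covers this case.
- Section 11.1.1 defines the primary endpoints through Ki67 and ER only, so it offers no rule here.

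The trial is single-arm, so no control group would reveal such cases. The decision thresholds are low (1 in 12, then 4 in 32), so each wrongly credited response carries weight.

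**Working it through.** **Inputs from section 12.1.** n1 = 12, stop at 0; n = 32, promising at 4 or more; null rate 0.05, target rate 0.20.

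**Step 1: reproduce the plan's figures.** With response rate p:

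- P(early stop) = (1 − p)^12
- P(promising) = Σ over x = 1 to 12 of P[Bin(12, p) = x] × P[Bin(20, p) ≥ 4 − x]

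| p | Early stop (stated) | Promising (stated) |
|---|---|---|
| 0.05 | 0.540 (0.54) | 0.065 (0.07) |
| 0.20 | 0.069 (0.07) | 0.866 (0.87) |

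All four agree. The design arithmetic is sound for a given total response rate.

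**Step 2: one biopsy-caused pCR among the first 12.** No frequency has to be assumed here. The continuation rule is met with certainty; under the 5% null it is otherwise met with probability 1 − 0.540 = 0.46. The combination is then promising if at least 3 of the other 31 patients respond. At 5%:

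P[Bin(31, 0.05) ≥ 3] = 1 − 0.95^31 − 31 × 0.05 × 0.95^30 − 465 × 0.05² × 0.95^29 = 1 − 0.204 − 0.333 − 0.263 = 0.20.

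This is about three times 0.065. It is conditional on such a case having occurred. If none of the other 31 responds, the count is 1 of 32 and the combination is not promising.

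**Step 3: averaged over an assumed frequency.** Let a be the share of all analysed patients whose tumour was cleared by biopsy and who are credited with pCR. The documents do not give a; the values below are assumptions. A cleared patient always counts and the rest respond at 5%, so the effective rate is a + 0.05(1 − a) = 1 − 0.95(1 − a). Putting this into the step 1 formulas:

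| a (assumed) | Effective rate | Early stop | False go | At least one case in 12: 1 − (1 − a)^12 |
|---|---|---|---|---|
| 0 | 0.0500 | 0.540 | 0.065 | 0 |
| 0.5% | 0.0548 | 0.509 | 0.085 | 0.06 |
| 1% | 0.0595 | 0.479 | 0.107 | 0.11 |
| 2% | 0.0690 | 0.424 | 0.157 | 0.21 |

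Only first-cohort patients have a surgical specimen, so a is diluted by the second cohort. If half the analysed patients were operable (also an assumption), a = 0.5% would correspond to 1% of operable patients.

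**The case against.** **Eligibility already excludes the obvious case.** Section 3.1.11 requires an unresected tumour, and a breast examination recording the mass is done at screening and scheduled again on Day 1. This stands in part. A reader might infer that patients whose tumour is known to be gone can enter and be scored as responders; the criterion bars that. What remains is clearance that nobody recognises until surgery, because no post-biopsy evidence of tumour is required.

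**The route is narrow.** Excisional biopsy is not listed, an incisional biopsy ordinarily samples part of a lesion, and the extra core applies only when tissue falls short of a small requirement. This bears on how often the event happens, not on how the rule would score it. Because the documents give no frequency, the averaged figures illustrate sensitivity and do not show that the effect is large.

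**The stated probabilities are not wrong.** A reader might infer that the 0.54 early-stopping figure fails. It does not: it is stated for a total success rate of 5%, and section 12.1 includes pCR in response. The narrower point survives. The sentence giving 0.87 and 0.07 names only the biomarker combination, so the plan does not show that its 5% null leaves room for pCRs caused by biopsy.

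**The second cohort is not affected.** A reader might infer that a metastatic core or aspirate that misses tumour would also be a pCR. The responder rule refers to surgical specimens, secondary objective 3 in section 1.2 concerns preoperative treatment, and section 11.1 concerns breast and axilla. The documents do not support that reading.

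**Any single response passes a 0-of-12 rule.** True, and one case cannot reach 4 of 32. The issue is that this particular response may carry no information about the drug.

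**Conclusion.** The concern holds, confined to first-cohort surgical specimens and to unrecognised clearance by the pre-treatment biopsy. Applied as written, sections 11.1.2 and 12.1 credit such a patient with a primary response.

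The firmest measure of size is conditional: one case in the first 12 guarantees continuation to stage 2 and, with 5% response in the others, puts the probability of a promising verdict at 0.20 rather than 0.065. The averaged range of 0.085 to 0.157 rests wholly on the assumed frequency of 0.5% to 2% of analysed patients.

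The stated operating characteristics remain correct for a given total response rate. What is unsupported is treating 5% as the null for a rule that also counts these cases. The change is worth making because the gap bears on the primary decision and costs little to close.

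**What to change.** In sections 11.1.2 and 12.1, state that pCR counts toward the primary response only in a first-cohort surgical specimen, and only where residual breast tumour was documented after the last pre-treatment biopsy. The evidence can be whatever post-biopsy imaging is available or the tumour measurement already in the study calendar. The wording must say explicitly that the evidence postdates the last biopsy, because section 10.3 lets a screening assessment within 3 days replace the Day 1 one. A patient with no tumour at surgery and no such evidence is not credited as a response and is listed separately; say whether she stays in the denominator.

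Report pCR-only responders separately from Ki67/ER responders, and report the 0-of-12 and 4-of-32 decisions also on the Ki67/ER criterion alone, which is the quantity named in the 0.87/0.07 sentence.

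The cost is a few sentences and one additional count, using data already collected. There are two drawbacks. Some true pCRs in non-palpable tumours without post-biopsy imaging will lose credit. Palpation after biopsy is also imperfect, since biopsy change can be mistaken for residual tumour. The Ki67/ER-only count is the backstop for that second weakness, although it gives no credit to a true pCR.

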9.1.1 Collections

In the first cohort:

Tumor tissue samples from the following time points will be obtained:

1. Prior to starting treatment or tissue sample at the original diagnostic procedure. (T0)
2. At the time of definitive surgery (i.e., mastectomy or lumpectomy). A separate tumor biopsy is not needed on the day of surgery; tissue will be taken from the surgical specimen. (T1)

Note: If a subject receives additional preoperative treatment after discontinuing study treatment and prior to surgery, every attempt should be made to collect a tissue sample for the study prior to initiation of the new treatment; in these cases, tissue will still be collected at the time of definitive surgery, as above.

Every effort should be made to provide a core specimen from the surgical sample after treatment. The site pathologist should remove a core samples during the dissection of the surgical specimen (using a 5-mm skin punch biopsy device). The samples should be processed preferably within 1 hour, but may be processed up to 2 hours of removal from the patients. This core specimen should be fixed in formalin and processed separately as per the American Society of Clinical Oncology/College of American Pathologists Guideline Recommendations published in Journal of Clinical Oncology 2010⁴².

In the second cohort:

Approximately six core biopsy specimens will be obtained with each biopsy. Alternative to core needle biopsy, fine needle aspirate (FNA) is allowed in this cohort of patients. Cytology cell blocks should be made from FNA specimens using routine institutional cytology protocol. Biopsy should be obtained from soft tissue metastasis such as breast, liver, skin, lung, or intra-abdominal implants. Bone biopsy, paracentesis (ascites), and thoracocentesis (pleural effusion) specimens are not adequate.

Tumor tissue samples from the following time points will be obtained:

1. Pretreatment biopsy (biopsy#1) will be performed within 3 weeks after registration. However, the pretreatment biopsy can be omitted in patients who have recent biopsy but have not been started on breast cancer treatment within 12 weeks prior to the registration and there is adequate tumor tissue sample as per section 3.1.9. (T0-Second cohort)

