2. Post-treatment biopsy (biopsy#2) will be performed after a minimum of 15 days and a maximum of 29 days of treatment, but preferably close to 29 days. The post-treatment biopsy must take place within 6 days (preferably within 3 days) after the last dose of entinostat. If a patient discontinues the study prior to 15 days, an attempt should be made to collect the biopsy when the decision is made to discontinue and prior to initiation of additional treatment, if possible.

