9.1.2 Paraffin Embedded Tissue Submission

All samples must be submitted **within ONE month** after the patient's definitive surgery or biopsy. All materials must be labeled with the institutional surgical pathology number, the study number, the patient's study number, the cohort number (first or second), the treatment group (tamoxifen or anastrozole), and the designated specimen type (T0 or T1). The samples should not contain patients' identifying information.

Please be sure to use a method of shipping that is secure and traceable. Extreme heat precautions should be taken when necessary. Please use papers to pad the specimen shipments. Do not use bubble wrap. Shipping should be arranged only on Monday-Thursday by overnight service to assure receipt. **Do not ship specimens on Friday or Saturday**. Please notify all of the contact persons listed below via email and/or telephone **PRIOR** to shipping.

A copy of the tissue tracking form should be included in the shipping package. Please note that if multiple samples are sent, only one copy of the form needs to be included.

The specimens should be shipped as directed below:

Specimens	Purpose	Shipping Address and Contact Information
≥3 unstained slides*	ER, PR, HER2, EGFR, CK5/6, Aromatase, histone H3, H4 acetylation, and Ki67 expression by immunohistochemistry NOTE: A copy of the pathology report from the treating and/or referring institution and a copy of the operative report should be included	[name], HT (ASCP) Pathology Biorepository and Research Core University of Maryland Medical Center [name] [name] 21201 [contact] [contact] Email: [contact]

	in this package.	
Tumor/lymph node block or ≥ 3 unstained slides[∞]	Gene expression profiling and Methylation profiling	[name]. Sidney Kimmel Comprehensive Cancer Center at Johns Hopkins [name] [contact] [contact] Email: [contact]

*Five-micron (5 μ M) thickness mounted on charged slides (do not oven bake slides) from both original diagnostic tumor blocks **AND** residual primary tumor or a positive lymph node blocks should be submitted as described above.

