9.1.3 Methods

9.1.3.1 Immunohistochemistry

Immunohistochemistry (IHC) will be used to determine the pre-treatment and post-treatment expression of ER, PR, HER2, and Ki67. The level of expression of these proteins will be quantified by ChromaVision ACIS Assisted Quantitative Image Analysis. These studies will be performed by immunohistochemistry technicians in the pathology department at the University of Maryland which is certified by both Clinical Laboratory Improvement Amendments (CLIA) and College of American Pathologists (CAP). The specimens will be de-identified with a unique patient's study number and stored in the tumor bank facility at University of Maryland. Hematoxylin and eosin stained sections will be examined by a pathologist to confirm the tissue source. Five-micron sections of formalin-fixed, paraffin-embedded tissue will be tested for the presence of immunohistochemically detectable ER, PR, HER2, and Ki67 expression. After 60 minutes of heat induced epitope retrieval in citrate buffer, streptavidin biotin detection systems using Ventana reagents and instruments will be used. We will use ER, PR, HER2, Ki67, EGFR, and CK5/6 antibodies that have been validated and are currently in clinical use at University of Maryland pathology department as listed below.

Immunostaining	Antibody
ER	SP1 rabbit monoclonal Ventana prediluted anti-ER antibody
PR	1E2 rabbit monoclonal Ventana prediluted anti-PR antibody
HER-2	4B5 rabbit monoclonal Ventana prediluted anti-HER-2/neu antibody
Ki67	30-9 rabbit monoclonal Ventana prediluted anti-Ki67 antibody
EGFR	3C6 mouse monoclonal Ventana prediluted anti-EGFR antibody
CK5/6	D5&16B4 mouse monoclonal Ventana prediluted anti-CK5/6 antibody
Aromatase	Mouse monoclonal antibody (Novartis #677) ⁴³

Scoring systems:

- ER and PR: Will be scored as the percentage of positive staining tumor nuclei on the examined slide. Five percent immunoreactivity is considered a positive result. This is based on comparison of our results to that of clinically validated ER and PR assays, determined by several large clinical studies.
- HER-2/neu: Will be scored as followed - score 0: no membrane staining is observed. 1+: weak, incomplete staining in any proportion of the invasive tumor cells. 2+: complete membrane staining in less than or equal to 30% of the invasive tumor cells. 3+: strong complete membrane staining in more than 30% of the invasive tumor cells.

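### The responder rule sets no baseline ER condition for lesions other than the ER-typed primary, so a lesion already ER-positive before treatment can count as ER upregulation

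*Combined protocol and SAP*

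**What the plan says.** Section 12.1 names the efficacy endpoints as "the reduction in proliferative index (Ki67) and upregulation of ER after treatment". The response definition that follows requires a Ki67 fall of at least 50% together with "greater than 1% ER-positivity OR pathologic complete response in the post-treatment surgical specimens". Ki67 is judged against baseline; ER is judged on the post-treatment sample alone. Section 11.1.1 also gives only a post-treatment ER threshold. The operating characteristics in 12.1 are nevertheless stated for a change: "If the true proportion of patients with Ki67 reduction combined with ER up-regulation is 0.20".

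The only ER condition before treatment is inclusion criterion 3.1.4: "Evidence of hormone insensitivity (ER and PR negative) of primary tumor tissue", with ER negative meaning below 1%. It applies to the primary.

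Other tissue can be read:

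- Second cohort, section 9.1.1: "Biopsy should be obtained from soft tissue metastasis such as breast, liver, skin, lung, or intra-abdominal implants". The post-treatment sample is a second biopsy: "Post-treatment biopsy (biopsy#2) will be performed after a minimum of 15 days and a maximum of 29 days of treatment".
- Either source, section 9.1.2, in the footnote to the immunohistochemistry slides: "residual primary tumor or a positive lymph node blocks should be submitted as described above".

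No section requires those lesions to be ER-negative before treatment, or the two samples of a pair to come from the same lesion. Section 12.1 pools both cohorts in one count, with success at 4 or more responses in 32.

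Two further inconsistencies bear on the rule. The ER cut-off is above 1% in 12.1 and at least 1% in 11.1.1, while 9.1.3.1 says "Five percent immunoreactivity is considered a positive result". And 11.1.1 places the Ki67 and ER reading in the primary breast tumour, which does not fit a biopsy of a metastasis or the pooling of both cohorts.

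**The concern.** A single post-treatment ER reading shows upregulation only if the lesion was known to be ER-negative beforehand. For a first-cohort patient read on the primary, 3.1.4 supplies that knowledge. For a metastasis or a node nothing does.

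A lesion with ER already above the cut-off passes the ER half whatever entinostat does. Every patient also receives anastrozole or tamoxifen, so the Ki67 half could be met through ordinary endocrine sensitivity. Such a patient would be counted as ER re-expression, and the response rate under no true re-expression would exceed the 5% on which the design rests. With a bar of four responses, one or two such patients matter.

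**Working it through.** **Inputs from section 12.1.** Stage 1 has 12 patients, stopping at 0 responses; stage 2 adds 20; success is at least 4 of 32. Null rate 0.05, target rate 0.20. Stated error 0.07, power 0.87, early-stopping probabilities 0.54 and 0.07.

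**Reproducing the plan.** P(promising | p) = Σ over x = 1 to 12 of Pr[Bin(12, p) = x] × Pr[Bin(20, p) ≥ 4 − x], the last factor being 1 when x ≥ 4.

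At p = 0.05: 0.3413 × 0.0755 + 0.0988 × 0.2642 + 0.0173 × 0.6415 + 0.0022 = 0.0652. At p = 0.20 the sum is 0.8665. Early stopping is 0.95^12 = 0.540 and 0.80^12 = 0.069. All four stated figures are confirmed, so the arithmetic of the design is not in question.

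**Exactly k already-positive lesions scored as responses**, placed at random among the 32, the other patients responding at 5%:

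- k = 1. If the patient falls in stage 1 (chance 12/32), P(promising) is 0.2008; if in stage 2 (20/32), 0.1648. Overall: 0.375 × 0.2008 + 0.625 × 0.1648 = 0.178.
- k = 2. With 0, 1 or 2 of them in stage 1 (chances 0.3831, 0.4839, 0.1331), P(promising) is 0.3241, 0.4465 and 0.4465. Overall: 0.400.

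These are conditional on such responses having occurred; they are not error rates of the design.

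**Unconditional illustration.** The documents do not say how often a lesion would be ER-positive at baseline, so two quantities are assumed: f, the share of all patients whose lesion is already ER-positive, and q, the chance that such a lesion shows a Ki67 fall of at least 50%. The null rate becomes p = 0.05(1 − f) + f·q. Example: f = 5%, q = 0.5 gives 0.0475 + 0.025 = 0.0725. P(promising) is then:

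| q | f = 1% | f = 3% | f = 5% | f = 10% |
|---|---|---|---|---|
| 0.05 | 0.065 | 0.065 | 0.065 | 0.065 |
| 0.2 | 0.071 | 0.084 | 0.097 | 0.135 |
| 0.5 | 0.084 | 0.127 | 0.178 | 0.327 |
| 0.8 | 0.097 | 0.178 | 0.275 | 0.532 |

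If half the patients were in the second cohort (also assumed) and all such lesions arose there, f = 1% to 10% corresponds to 2% to 20% of second-cohort lesions.

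**What the documents offer on q.** Section 2.6 cites a 76% geometric mean Ki67 reduction at 2 weeks on anastrozole in previously untreated postmenopausal women with ER-positive disease. That supports the direction. It is a mean, not the proportion reaching a 50% fall, and it comes from a different population.

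**The case against.** The strongest reply is that the size is assumed. The documents give neither a rate of ER discordance between primary and metastasis nor the second-cohort share, and the table begins at no inflation at all. The Ki67 requirement is a real filter: second-cohort patients have had chemotherapy, premenopausal patients receive tamoxifen, and nothing shows that a lesion just above 1% ER would lose half its Ki67. This stands, and it is why only the direction is claimed.

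The phase II objective in 1.1 speaks of ER expression after treatment, which matches a post-treatment threshold. But 12.1, which holds the decision rule and its design rates, calls the quantity up-regulation, and the objective does not change that.

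Section 11.1.1 could be read as confining the endpoint to the primary, which weakens the nodal route in the first cohort. Applied literally, though, it would leave patients biopsied at a metastasis unassessable while 12.1 includes them. The gap is mainly a second-cohort one.

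Baseline ER is measured (9.1.3.1) and compared in 12.3, so a baseline-positive responder would be visible in the data. That comparison is of group averages and does not enter the 4-of-32 decision.

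Finally, 3.1.4 does not say that the eligibility reading is central, and a central baseline rule for everyone reaches further than the gap. That is fair. A uniform rule is simpler, and patients read on an ER-negative primary should normally satisfy it.

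**Conclusion.** The concern holds and should be fixed. As written, the rule can count a lesion that was ER-positive before treatment towards the primary decision, under an endpoint named and powered as ER up-regulation. The plan's operating characteristics are correct for the rates it states; what is uncertain is whether 5% is the right null rate for the rule as worded.

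One such response raises the chance of a promising verdict from 0.065 to 0.178, and two raise it to 0.400. Across the assumed f of 1% to 10% and q of 0.05 to 0.8, the probability runs from 0.065 to 0.532. Confidence is medium: the definitional gap is plain in the text, but its practical size depends on values that the documents do not contain. The conflicting cut-offs and specimen descriptions need reconciling in any case.

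**What to change.** - In 12.1 and 11.1.1, define ER response as conversion: centrally read baseline ER below 1% and post-treatment ER of at least 1%. Use that one cut-off for the endpoint throughout, and reconcile the 5% in 9.1.3.1 with it.
- Read ER and Ki67 on paired samples from the same lesion where available. Flag pairs from different sites, including nodal blocks, and repeat the 4-of-32 analysis with those patients counted as non-responders, as a sensitivity analysis.
- Keep patients with central baseline ER of 1% or more in the denominator, count them as non-responders on the ER/Ki67 route, and list them. Leave the pathologic complete response route unchanged.
- State that the second-cohort post-treatment specimen is the second biopsy, and reconcile the references to the primary breast tumour (11.1.1) and surgical specimens (12.1) with 9.1.1.

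**Cost.** Wording only. Baseline ER staining is already planned centrally, and baseline tissue is needed for the Ki67 change anyway. If the affected patients would otherwise have responded at 20%, power becomes P(promising | 0.20(1 − f)): 0.861, 0.851, 0.839 and 0.807 for f = 1%, 3%, 5% and 10%, against 0.866 now. The corresponding error, at 0.05(1 − f), is 0.063, 0.060, 0.056 and 0.048. Treating these patients as inevaluable would avoid the power loss but would draw on a margin of only 35 − 32 = 3 patients.
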